## 7.) Pain Anxiety Symptoms Scale-short version

The Pain Anxiety Symptoms Scale-short version (PASS-20) measures pain-related fear, anxiety and avoidance and it contains four subscales: cognitive anxiety, escape/avoidance, fearful thoughts and physiological anxiety (McCracken and Dhingra, 2002). Each subscale contains five items; and items are rated on a 6-point Likert scale (0='never' and 5='always'). The subscales of the PASS-20 have demonstrated good internal consistency and convergence validity with the PASS-40 (McCracken and Dhingra, 2002).

#### 8.) 12-Item Short-Form Health Survey

The 12-Item Short-Form Health Survey (SF-12) is a generic health survey that assesses physical and mental function (Ware et al., 1996). The 12 items are scored out of 100, where higher scores indicate better function. The SF-12 correlates highly with the original 36-item survey and it has demonstrated test-retest stability (Ware et al., 1996; Jenkinson et al., 1997).

#### 9.) EuroQol (EQ-5D-5L)

The EuroQol (EQ-5D-5L) is a generic measure of health status that is widely used to assess both clinical and economic efficacy; and to compare health status across diseases (Brooks, 1996; Devlin and Brooks, 2017). The EQ-5D-5L measures health related quality of life via dimensions of mobility, self-care, usual activities, pain and anxiety/depression (Devlin and Brooks, 2017). The EQ-5D-5L was developed to reduce the possible ceiling effects of the EQ-5D-3L which contained only three levels of answers to each question (Devlin and Brooks, 2017).

The T2 and T3 booklets will contain the same questionnaires, except without the demographic questions. The T2 booklet will additionally contain two 11-point numerical rating scales (0-10) regarding satisfaction of the programme content and length. The T2 questionnaire booklet will also include a question inviting participants to indicate whether they would be interested in participating in the acceptability interviews (see Appendices 6, 7, 8 and 9 for the T1\_Post, T1\_Dept, T2 and T3 questionnaire booklets respectively; and Appendix 10 for the covering letter for T3).

Participants will be asked to complete a 1-week activity diary after activity pacing is introduced in the rehabilitation programme. The diaries will be used the following week to assess patients' patterns of behaviour, and to set goals towards pacing that are individualised. (See Appendix 5: Activity Pacing Framework 'Appendices and Teaching Guide' for the activity diaries.)

#### 2.2.3.2 Process evaluation

The Medical Research Council advise a process evaluation of complex interventions to explore the credibility of the findings and any confounding factors that may influence the outcomes (Moore et al., 2015). The process evaluation of the development of the activity pacing framework will include patients' completion of NRS rating scales of satisfaction of the rehabilitation programme, and general comments that are made in the questionnaire booklets. The satisfaction ratings will assist the selection of participants for the next stage of the study: the acceptability interviews, which will discuss the programme in more detail.

Healthcare professionals will be asked to complete a rehabilitation programme checklist to explore their compliance with the framework (see 'Appendices and Teaching Guide' Appendix 12 for the checklist). The Chief Investigator will meet healthcare professionals to ensure that there are no issues with delivering the activity pacing framework. Furthermore, the Chief Investigator will observe the rehabilitation programme at the different locations to monitor compliance with the study protocol and activity pacing framework. The Chief Investigator will be observing for a checklist of key points that are included in the delivery of the pacing framework in the rehabilitation programme (see Appendix 11 for the Chief Investigator's checklist)

#### 2.2.4 Data analysis

Descriptive statistics will summarise the demographics of the sample, and compare between patients who complete/do not complete the programmes and between the hospital locations. The feasibility study will not be powered to detect clinically important or statistically significant effects. Analysis will focus on estimating confidence intervals and effect sizes for differences in means or medians to inform the design of future trials, together with indicating likely recruitment/retention/compliance rates. The IBM SPSS Statistics 24 program will be used to analyse the data.

REC ref: 18/LO/0655

## 2.3 Stage III: Acceptability qualitative study

## 2.3.1 Sampling principles and procedures

#### 2.3.1.1 Participants

The acceptability of the pacing framework/rehabilitation programme will be discussed in semi-structured telephone interviews with a sample of the patients and healthcare professionals (physiotherapists and psychological wellbeing practitioners) who were involved in the feasibility study.

#### Inclusion criteria:

- Patients with an initial GP/hospital consultant referral to The Pennine
  Acute Hospitals NHS Trust with diagnoses of chronic low back pain,
  chronic widespread pain, fibromyalgia or CFS/ME, with a minimum
  symptom duration of 3 months (as per the feasibility study).
- Patients who attended a minimum of the first two sessions of the rehabilitation programme, who consented to the study and completed the first questionnaire booklet. Patients do not need to have completed the programme, since the interviews will include patients who both completed and did not complete the programme.
- Qualified healthcare professionals delivering the rehabilitation programmes who received training in using the activity pacing framework: physiotherapists and psychological wellbeing practitioners employed by The Pennine Acute Hospitals NHS Trust and Pennine Care NHS Foundation Trust.

#### **2.3.1.2 Sample size**

Patients and healthcare professionals participating in the feasibility study will be invited to participate in the interviews until there is a sample of approximately 15-20 patients and 6-8 healthcare professionals, or when data saturation is reached. Purposive sampling of patients will be undertaken to recruit patients with chronic low back pain, chronic widespread pain/fibromyalgia and CFS/ME; patients who were satisfied/unsatisfied with the programme (using the satisfaction scale in the T2 questionnaire booklet completed in the last week of the programme); and patients who did/did not

complete the programme. Used in this way, purposive sampling will enable wider discussions into both the favourable and less favourable opinions regarding the programme to enable the framework/programme to be further developed in the future. Purposive sampling with healthcare professionals will ensure that both physiotherapists and psychological wellbeing practitioners are invited to be interviewed.

#### 2.3.1.3 Recruitment

Potential participants will be identified from those patients who tick the check box to agree to be contacted for an interview in the T2 questionnaire booklet (completed on the last week of treatment). In order to invite patients who did not complete the programme to participate in the interviews, patients who consented to the feasibility study, completed the first questionnaire (T1) and attended a minimum of the first two sessions of the programme will also be contacted. This will allow patients who did not complete the programme to discuss any barriers or challenges that arose. All patients, whether they completed the programme or not, will be invited to participate in the interviews over the telephone by the Chief Investigator. Patients who are interested in participating in the interviews will be sent a letter of invitation, an information sheet explaining the aims/nature of the interviews and that the interviews will be digitally recorded, together with a consent form (see Appendices 12, 13 and 14 respectively).

Healthcare professionals will be invited to participate in the interviews either in person, or via email/phone. They will be given an information sheet explaining the aims/nature of the interviews, and that the interviews will be digitally recorded (see Appendices 15 and 16). Healthcare professionals will be asked to sign and date the consent form and complete some basic demographic information (age, gender, profession and duration of expertise in chronic conditions) (see Appendices 17 and 18).

Both patients and healthcare professionals will be asked to sign the consent forms and return them in pre-paid envelopes within one week. They may receive a telephone call if no contact has been made within one week to ask if

they still wish to participate in the interviews. They will also be asked to confirm their consent at the start of the audio-recorded interviews.

#### 2.3.2 Data collection methods

#### 2.3.2.1 Outcome evaluation

The interviews with patients will be held once they have stopped attending physiotherapy: either through their completion or non-completion of the programme. It is therefore envisaged that the interviews will occur approximately two months after recruitment commences for the feasibility study (see Figure 2. Timetable of the study). Patients will be invited to participate in either telephone or face-to-face semi-structured interviews by the Chief Investigator (DA). Face-to-face interviews will be undertaken by the Chief Investigator (DA) in the physiotherapy departments or patients' homes according to their preferences. If the interviews occur in patients' homes, The Pennine Acute Hospitals NHS Trust lone-worker policy will be followed. The interviews will discuss the content of the programme, the information regarding pacing, patients' opinions/experiences of pacing, the use of activity diaries and goal setting sheets, and the ease of completing the questionnaire booklets. Discussions will also involve identifying any potential barriers with attempting/committing to pacing, for example, symptoms or habits.

The interviews with healthcare professionals will be held throughout the period of data collection for the feasibility study. Telephone or face-to-face semi-structured interviews will be used according to healthcare professionals' preferences and availability. Face-to-face interviews will be undertaken by the Chief Investigator (DA) and they will occur in the physiotherapy departments or healthcare professionals' homes. The interviews will discuss the content and clarity of the framework and its usability in the clinical setting. The interviews will discuss any barriers to adherence with the pacing framework (for example, patients' symptoms or practical issues). (See Appendices 19 and 20 for the interview outlines for patients and healthcare professionals). The interviews with all participants are envisaged to last between 20-60 minutes. Interviews will be digitally recorded and transcribed verbatim. Both

patients and healthcare professionals will be invited to read and check their own transcription for accuracy and invited to receive a report of the findings.

#### 2.3.2.2 Process evaluation

Qualitative interviews are considered to be a useful method of process evaluation of complex interventions (Moore et al., 2015). The qualitative acceptability interviews will explore the fidelity of the feasibility stage with regards to adherence by both the patients and healthcare professionals to the activity pacing framework/rehabilitation programme. The interviews will help to identify possible contextual factors between patients/clinicians/locations/number of sessions that may influence the findings. This process will assist the development of future studies that implement the pacing framework.

#### 2.3.3 Data analysis

The qualitative data from the interview transcriptions will be analysed using Framework analysis. Framework analysis is a five-stage iterative matrix method, considered to be comprehensive and transparent, and allows for both inductive and deductive data analysis methods (Ritchie et al., 2003). The NVivo program (Version 11) will be used to manage the qualitative data.

Data analysis commences during the undertaking of the interviews and the transcription, and continues during analysis of the transcriptions. The early commencement of data analysis during data collection/transcription facilitates the development of subsequent interviews and the detection of data saturation when no new concepts emerge (Morse and Field, 1996). Data analysis will be undertaken by the Chief Investigator working alongside a researcher ([name]) with an expertise in qualitative research methods, together with two patients who are sitting on the study advisory panel.

#### 2.4 Refining the activity pacing framework

Key findings from the feasibility and acceptability studies will be used to refine the pacing framework. Data from the feasibility and acceptability outcome evaluations will be synthesised using a seven-stage process in keeping with convergent mixed methods data analysis (Creswell and Piano-Clark, 2011). This process will commence with separate data analyses of the feasibility questionnaire data and the qualitative interviews using quantitative and qualitative methods respectively. Key points for comparison between the quantitative and qualitative data will be determined. Once the data have been compared, the findings will be merged and interpreted. This synthesis of databases is beneficial to the validation of the findings through the triangulation of data from different sources (Creswell and Piano-Clark, 2011).

The validity of the feasibility data will be limited since the sample size will be too small to infer statistical changes in pacing or symptoms. However, some patterns may arise in the quantitative data. The findings from the qualitative interviews may help to explain some patterns in the quantitative data. Findings from the synthesised data will help to refine the pacing framework and the definition/model of pacing. For example, it may emerge that some facets or aims of pacing are more frequently implemented or possibly mis-interpreted. Such elements may require a greater or lesser emphasis in the framework.

The activity pacing framework will be further refined using the findings from the process evaluations. The process evaluations include the healthcare professionals' checklist of compliance, Chief Investigators' checklist of observations of the programme and feedback from the meetings with the healthcare professionals, together with aspects of the acceptability qualitative interviews (for example, regarding compliance/adherence). The process light practical problems of evaluation may bring to framework/appendices which can be modified to increase the usability of the framework. The process evaluation may also show differences in the programme delivery and adherence across different locations/ clinicians/duration of programme (five/six weeks); differing levels of acceptability across patients with different conditions; or possibly different changes in symptoms across different locations/conditions. Such findings could refine the framework through the acknowledgement of such potential differences/barriers and suggestions of methods to address discrepancies.

The rate of attrition of the programmes, the completion of the questionnaire booklets (T1, T2 and T3), and the completion of activity diaries/goal setting sheets will be used to re-consider the format, length, burden and usability of these documents in the clinical setting. Information regarding attrition and compliance will help to modify the appendices and the questionnaire booklets to improve their usability in order to maximise recruitment and retention rates, and to improve the experience for patients and healthcare professionals in future studies. As a feasibility study, the purpose is to test the framework and methods of recruitment in order to prepare for a future clinical trial.

#### 3.0 ETHICAL AND REGULATORY CONSIDERATIONS

#### 3.1 Assessment and management of risk

It is not expected that participants will be at any risk from participating in the study. Patients' participation in the feasibility study involves their completion of questionnaires at the beginning, end and at 3-months follow-up of their attendance of a rehabilitation programme. Rehabilitation programmes have been running in the physiotherapy departments at these sites for over a decade and the healthcare professionals running the groups are experienced in delivering these programmes. The activity pacing framework will standardise and structure the instructions of a coping strategy that is usually discussed in the programmes.

Contained within the feasibility questionnaire booklet is a measure of depression (PHQ-9) which asks one question regarding suicidal ideation. If patients indicate that they have suicidal thoughts, this will be managed according to the usual risk pathway within the hospital sites. Patients will have access to the psychological team, step-up services/emergency telephone numbers or advised to attend the Emergency Department.

During the acceptability interviews, no risk of harm is expected for either patients or healthcare professionals. The subject of the interviews: the activity pacing framework, is not considered to be sensitive or upsetting. However, if either the acceptability or feasibility studies have the potential to harm the well-being of an individual, they will be withdrawn from the study immediately and interviews will be stopped appropriately should sensitive/upsetting discussions arise.

In the case of any adverse event, this will be documented following the usual protocol in The Pennine Acute Hospitals NHS Trust incident reports. The Research Ethics Committee will also be notified.

REC ref: 18/LO/0655

#### 3.2 Benefits

Participants will be advised that they may not receive any direct benefit from participating in the study. However, the information gathered from the study will contribute to the development of future practice and treatment.

# 3.3 Research Ethics Committee (REC) and other regulatory review and reports

The study will be conducted in accordance with the UK Policy Framework for Health and Social Care Research and other applicable guidance. The study will not commence until all regulatory approvals are in place, which will include HRA approval, REC approval and confirmation from local R&D that the Trust/s have Capacity and Capability to carry out the research.

The Chief Investigator will complete and submit annual progress reports to the Sponsor as requested and prior to submission to NHS REC, in accordance with the terms and condition of the study approval.

The study will be subject to the standard procedures for monitoring and auditing of studies by the sponsor.

Any changes to the protocol will be agreed with the sponsor prior to submission to NHS research ethics committee for review with the exception of where urgent safety measures apply.

All staff working in the study will have completed appropriate training to undertake the duties delegated to them by the Principal investigator such an ICH-GCP.

#### 3.4 Patient and Public Involvement

Patient and public involvement (PPI) commenced in the original development of the study to develop an activity pacing framework before Stages I and II. The current study is guided by a research team, together with an advisory team who comprise of two patients with chronic pain/fatigue and two clinicians. In the preparation of Stage III of the study, PPI have been involved

in commenting on the study documents, for example, patient information sheets, the activity pacing framework and questionnaire booklets. PPI will also be invited to work alongside the researchers during the qualitative data analysis from the acceptability interviews.

#### 3.5 Data protection and patient confidentiality

In Stage III: Feasibility study, all patients will be identified using unique study codes. Healthcare professionals will also be identified using study codes so that their checklists can be collected anonymously. These study codes will be carried forwards for those who are involved in the Stage III. Acceptability interviews.

Throughout the data analyses for the feasibility and acceptability studies, participants' data will be identified by these unique codes on SPSS data files. Participants' codes and personal data (such as addresses/telephone numbers) will be kept secure on a password protected Microsoft Excel worksheet housed in a password enabled and encrypted laptop, and on The Pennine Acute Hospitals NHS Trust secure network. This information is required to invite patients to complete the 3-months follow-up questionnaire and to participate in the acceptability interviews.

The data will be stored for 10 years after data collection or the last publication, whichever date is the latter. This is with the exception of participants' personal data which will be removed from the password enabled and encrypted laptop as soon as it is no longer required.

Those patients who do not consent to the study will also be allocated a unique study code. However, no personal information regarding name, address, date of birth or NHS/department number will be stored on the Excel spreadsheet. Basic information from those patients who do not consent to the study, for example, age, main condition, ethnicity and duration of condition will be entered onto an SPSS data file to allow estimates of the representativeness of those patients who consent from all of those who attend the programme. These data will be anonymised using the unique study codes, and they will

not be linked to patients' records or to information regarding their identifiable data.

## 3.6 Dropouts/Withdrawals

Participants will be advised that they are free to withdraw from the study at any point without explanation. Where possible, the reason for withdrawal will be recorded. Once participants have completed the feasibility or the acceptability study, they may be able to withdraw their data. However, participants will be advised that this will only be possible before data analysis has commenced (month 15) since data analysis will involve the convergence of data (see Figure 2. Timetable of research activities).

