## 3.9 Conflict of interest

The Chief Investigator (DA) will be involved in recruitment, data collection, data analysis and dissemination. To reduce bias, the Chief Investigator will not be responsible for delivering the rehabilitation programmes.

The Chief Investigator, [name], is funded by an HEE/NIHR ICA Clinical Lectureship award (ICA-CL-2015-01-019). There is no conflict of interest.

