#### 6.0 TIMETABLE

## **Key milestones:**

**Project start:** Ethical approval received and agreement with The Pennine Acute Hospitals NHS Trust Research and Development Department.

**Month 1:** Feasibility study: train healthcare professionals in using the activity pacing framework (half-day training).

Feasibility study: Begin contacting patients enrolled in rehabilitation programmes to invite them to participate (T1). Recruitment and T1 data collection will continue for 15 months.

**Month 2:** Feasibility study: commence T2 data collection at the end of the 5/6-week's rehabilitation programme. T2 data collection will occur for 16 months.

**Month 3:** Acceptability study: Commence recruitment for semi-structured interviews. Conduct the interviews and analyse the qualitative data during data collection. Continue for 15 months or until data saturation is reached.

**Month 4:** Feasibility study: 3-months follow-up (T3) data collection commences. Continue for 17 months or until a suitable sample size is reached (aiming for n=50)

**Month 15:** Feasibility study: data analysis of quantitative data and writing up the findings

Acceptability study: write up the findings

**Month 16:** Refine the activity pacing framework

Develop the pacing definition and conceptual model.

(See Figure 2. Timetable of research activities)

Study duration:	1	2	3	4	5	6	7	8	9	10	11	12	13	14	15	16	17	18	19	20	21	22
22 months																						
Stage III. Feasibility study																						
Train healthcare	Χ																					
professionals using the	'																				'	
framework																						
Patient recruitment	Χ	Χ	Х	Х	Χ	Χ	Χ	Χ	Χ	Χ	Χ	Χ	Χ	Χ	Χ							
Data collection: questionnaire administration: T1 (initial)	X	X	X	X	X	X	X	X	X	X	X	X	X	Х	Х							
Data collection: questionnaire administration of T2 (6 weeks)		X	X	X	X	X	X	X	X	X	X	X	X	X	X	X	X					
Data collection: questionnaire administration of T3 (3 months follow-up)				Х	Х	Х	Х	Х	Х	Х	Х	Х	X	Х	Х	Х	Х	Х	Х	Х		
Data analysis															Χ	Χ	Х	Х	Χ	Х	Χ	Х
Write up study															Х	Χ	Х	Х	Х	Χ	Χ	Х
Stage III. Acceptability study																						
Recruitment			Х	Х	Χ	Х	Χ	Χ	Х	Χ	Х	Х	Х	Х	Х	Х	Х					
Data collection (interviews)			X	X	X	X	X	X	X	X	X	X	X	X	X	X	X					
Data analysis			X	X	X	X	X	X	X	X	X	X	X	X	X	X	X					
Write up study															Χ	X	X	Χ	Χ	Χ		
Refine pacing framework																X	X	X	Х	Х	Х	X
Develop pacing definition and conceptual model																X	X	X	X	X	X	X

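### Does closing data withdrawal at month 15, while interviews run to month 17 and T3 to month 20, call for a change to the plan?

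*Combined protocol and SAP*

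**What the plan says.** Section 3.6 gives two separate rights. Participants may leave the study whenever they like, without giving a reason. In addition, "Once participants have completed the feasibility or the acceptability study, they may be able to withdraw their data". The limit on this second option is that "this will only be possible before data analysis has commenced (month 15" in the timetable. The same sentence gives the reason: the analysis will bring the data together. It refers the reader to Figure 2.

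The milestones in section 6.0 set these periods:
- **Recruitment and T1:** "Recruitment and T1 data collection will continue for 15 months", that is, months 1-15.
- **Interviews**, from month 3: "Continue for 15 months or until data saturation is reached", that is, up to month 17.
- **T3**, from month 4: "Continue for 17 months or until a suitable sample size is reached (aiming for n=50"), that is, up to month 20.
- **Quantitative analysis:** from month 15, and in Figure 2 through month 22.

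For the interviews, section 2.3.3 says "Data analysis commences during the undertaking of the interviews and the transcription", and Figure 2 shows that analysis from month 3. Section 2.3.2.1 adds that "patients and healthcare professionals will be invited to read and check their own transcription for accuracy". Section 3.9 states that the Chief Investigator "will be involved in recruitment, data collection, data analysis and dissemination" but does not deliver the programmes.

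**The concern.** Read against the timetable, the limit falls before many participants can meet its condition. Nobody recruited in month 15 can have completed T3 by then. Someone interviewed in months 15-17 would check a transcript after the option to remove it had lapsed. For interviewees, the words and the date also disagree: analysis starts in month 3, not month 15. Since participants are to be told of the limit, the mismatch could reach the information they receive.

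A second worry is attached. The Chief Investigator takes part in both data collection and analysis, T3 answers may be taken by telephone (section 2.2.3.1), and quantitative analysis opens while T3 is still being collected. The plan does not say which analyses wait for T3 to close. If early results influenced later collection or the refinement of the framework, the estimates meant to inform a future trial could be affected.

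**Working it through.** **Inputs.** Section 2.2.1.3 gives 340 invited, 50% recruited, 60% completing the programme and 50% returning T3. It plans 216 invitations over 15 months at the first site and 168 over 12 months at the second. Section 6.0 gives the periods listed above. Even accrual, and a second site recruiting in months 4-15, are assumptions.

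**The plan's own figure.** 50 / (0.50 × 0.60 × 0.50) = 333, against 340 stated. Forward, 340 × 0.15 = 51 T3 completers from 340 × 0.50 = 170 consenters. The sample-size arithmetic reproduces.

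**Share of T3 completers past the limit, by month count.**
- T3 months 15-20 out of months 4-20: 6/17 = 35%, or 18 of 51.
- If the limit is the end of month 15: 5/17 = 29%, or 15 of 51.

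**The same share, by patient flow.** T3 falls five or six weeks plus three months after the start of the programme, a lag of about 4.15 to 4.4 months.
- Even accrual, limit at the start of month 15 (14 months elapsed): 1 − (14 − 4.15)/15 = 34% and 1 − (14 − 4.4)/15 = 36%.
- Even accrual, limit at the end of month 15: 1 − (15 − 4.15)/15 = 28% and 1 − (15 − 4.4)/15 = 29%.
- Later second site, limit at the start of month 15. The second site alone gives (15 − 9.85)/12 = 43% and (15 − 9.6)/12 = 45%. Weighted by 216 and 168 of 384, the totals are 38% and 40%.
- Later second site, limit at the end of month 15: 31% and 33% by the same weighting.

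The range is 28-40%, or 14 to 20 of 51. As a share of consenters it is 14/170 = 8% to 20/170 = 12%.

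**Early stopping of T3.** At the planned rates, the 50th of 51 returns arrives at about 50/51 × 15 + 4.4 = 19.1 months. Stopping at 50 therefore hardly reduces the share.

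**Interviews.** Months 15-17 are 3 of the 15 scheduled months, or 20%. The planned total is 15-20 patients plus 6-8 professionals, so 21-28 people, of whom about 4 to 6 fall in those months. Saturation before month 17 would lower this.

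**Effect on results.** The date of the limit enters no formula. Even if a later limit led one T3 completer to remove their data, the confidence interval for a mean would widen by a factor of √(51/50) = 1.01.

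**Start of T3.** A six-week programme starting on day 0 has its last session on day 35. Adding 91 days gives day 126, and month 4 ends at about day 122. Counting three months as 12 weeks gives day 119, inside month 4. On a monthly grid this is rounding.

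**The case for a change.** The strongest case for a change is that removal of data after completion is a distinct option with its own deadline, and that roughly a third of those who complete T3 can never use it. The general right to withdraw does not fully replace it, because section 3.6 does not say what happens to data already given when someone leaves. The stated reason also fits a later date: section 2.4 puts the merging of the two data sets after their separate analyses, so a limit at the start of analysis is earlier than the reason requires. For interviewees, the phrase about analysis starting and the date of month 15 cannot both be literal.

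The date mismatch and the loose wording stand. The harm is smaller than it looks. The text says only that completers may be able to remove data, and it tells them the limit at the same time, so nothing is promised and then withdrawn. The stated month is explicit, so staff have a usable date for interviewees even though coding starts earlier. What the information sheets say cannot be judged, because they are not in the documents available here.

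On the overlap of analysis and collection, the plan could have listed which analyses wait. But there is one arm, so there is no allocation to unblind. Section 2.2.4 plans estimates and confidence intervals and disclaims power to detect effects. The milestone for stopping T3 early depends on the number of returns, not on results. Section 2.3.3 adds a second researcher and two patients to the qualitative analysis. Analysis runs to month 22, and nothing says that T3 change estimates are produced in month 15. Analysts would naturally begin with cleaning, recruitment figures and baseline summaries.

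**Conclusion.** No change is needed. The limit in section 3.6 does not match the timetable: about 28-40% of the 51 expected T3 completers (14 to 20 people, or 8-12% of 170 consenters) would finish after it, and up to 20% of interviewees. These shares assume even accrual, the planned response rates and interviews spread evenly to month 17.

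Rewording the limit would tidy the text but bring no statistical gain, since no estimate, precision, bias, safety matter or conclusion turns on it. The order of analyses between months 15 and 20 is ordinary unwritten detail in a single-arm estimation study. Holding the T2 and T3 change estimates until T3 closes would leave only months 21 and 22 for them, and would delay their use in refining the framework, which starts in month 16. The present schedule is a fair trade-off. The question of T3 starting in month 4 or month 5 is rounding.
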